1. ETHICS COMMITTEE APPROVAL

The study will be conducted in accordance with this protocol, following its re- approval by the manager of Mayanei Hayeshua Medical Center. The study will be conducted in accordance with Procedure No. 14 ("Clinical Trials Procedure") of the Department of Pharmaceutics, Ministry of Health, Israel. Approval of both the protocol and the consent form will be obtained before any participant is enrolled.

2. ABBREVIATIONS

SRP – Scaling and root planing

RSD – Root surface debridement

PW – Peptone water

3. INTRODUCTION

3.1. BACKGROUND

Periodontal disease, affecting large proportion of adult population^{1,2}, both females and males, can lead to formation of spaces between the gingiva (gums) and teeth, called periodontal pockets, which occur due to loss of attachment between the gingiva and the teeth, mainly due to the inflammatory reaction to bacterial colonization on the teeth and gingiva^{3,4,5}.

Bacteria, which penetrate the pockets once they are formed, cause further inflammation and may deepen the pockets by creating further damage to the tissues and bones around the teeth^{3,5}. Probing the depth of the periodontal pocket is a good indicator for diagnosing the extent of periodontal disease. In a healthy periodontium, there is no loss of epithelial attachment or pocket formation, and the space between the gingiva and the teeth is less than 2 mm deep⁶.

Currently available conventional treatment for periodontal pockets includes root surface debridement (RSD) or scaling and root planing (SRP), which remove subgingival plaque and tartar, thus removing the causative factor for periodontitis while allowing the natural healing of the gums and sealing of periodontal pockets. However, new bacteria can infiltrate the pockets after RSD or SRP and inhibit the healing process.

In order to improve the healing of the gingiva and prevent relapse of inflammation within the periodontal pockets, adjunctive treatments have been developed, intended for application following RSD or SRP. These methods include antimicrobial laser therapy, host-modulating agents that inhibit host collagen-degrading enzymes which cause tissue loss due to inflammatory response, or use of antibiotic or antibacterial agents that assist in the inhibition of bacterial re-colonization inside the periodontal pockets. The latter are available either as rinses, toothpastes or sustained-release products, which are inserted into the periodontal pockets and remain inside for days or weeks. Additionally, systemic antibiotics may be administered with or without topical treatment. Other adjunctive treatment option

is use of barrier agents that fill the periodontal pockets and prevent infiltration of bacteria from the oral cavity into the pockets.

While the efficacy of SRP has been proven to be statistically significant in numerous clinical studies^{7,8}, various adjunctive treatments have been shown to provide greater improvement in clinical parameters such as probing pocket depth and clinical attachment level^{9,10,11,12,13}.

3.2. STUDIED DEVICE

The studied device, Pocket-X Gel, manufactured by Israeli-based Tree of Life Pharma Ltd., is an *in-situ* gelling device, used as physical barrier against bacterial re-colonization of the periodontal pockets following root surface debridement or scaling and root planing. Pocket-X Gel is provided in a pre-filled syringe along with 2 tips. It is applied to the periodontal pocket by a dentist using the provided syringe bearing one of the tips. It is applied in the form of a liquid, which transforms into a gel once placed in the periodontal pocket, due to contact with body temperature. The gel fills the periodontal pocket and prevents bacterial infiltration into the pre-cleaned pocket. One syringe can be used for multiple periodontal pockets present in the mouth of the same patient. The syringe or tip cannot be used on a different patient.

Pocket-X Gel contains the following components: Water, Poloxamer 407, Hyaluronic Acid, Phenoxyethanol, Octenidine Dihydrochloride.

The device is biodegradable. It remains within the periodontal pocket for a period of 1-3 weeks, afterwards it is either degraded or ejected from the pocket following natural sealing of the pocket as part of the gums healing process.

Pocket-X Gel only contains materials that are commonly used in oral products and are considered safe for oral use based on available literature. Additionally, *in-vivo* animal experiments conducted with the product at a GLP-certified laboratory indicated no irritation or sensitization. It is therefore expected that treatment with Pocket-X Gel will present a high safety profile during the study.

Furthermore, the product's application in the form of a liquid and its transformation into a gel only after its application allows to the product to perfectly fit the pocket's dimensions and shape. In addition, the product is applied through a thin and flexible plastic tip that does not traumatize the surrounding tissues. It is therefore expected that the product and its administration process will cause no discomfort to the patient.

3.3. STUDY DESCRIPTION AND RATIONALE

This study is a prospective open-label study in which Pocket-X Gel will be applied to periodontal pockets in one/two mouth segments of participants following scaling and root planing on the entire mouth, while the contralateral segment(s) of the mouth will serve as control.

The purpose of this study is to examine the safety and efficacy of Pocket-X Gel in the treatment of periodontal pockets, following scaling and root planing procedure.

The study's hypothesis is that Pocket-X Gel, when inserted into periodontal pockets following scaling and root planing procedure, would lead to greater improvement in periodontal clinical measurements such as pocket depth, bleeding upon probing, clinical attachment level, etc., in comparison to periodontal pockets which have undergone scaling and root planing only.

Pocket-X Gel is inserted into the periodontal pockets as a liquid. Following application, the product quickly transforms into a gel, due to contact with body temperature, and adheres to the inner lining of the periodontal pockets. This *in-situ* transformation from liquid form to gel allows Pocket-X Gel to fit into periodontal pockets of all sizes while completely filling the pockets. It is hypothesized that Pocket-X Gel, once inside the periodontal pocket, would act as a physical barrier against infiltration of bacteria originating from the oral cavity into the pocket, thus contributing to the greater improvement in the clinical state of the periodontal pocket.

The preceding procedure, scaling and root planing, is a conservative treatment which is considered the gold standard treatment of periodontitis in the majority of cases. As part of this procedure, the patient undergoes mechanical debridement which removes subgingival plaque and tartar, resulting in significant reduction of the bacterial load in the periodontal pockets. Subsequently, the inflammation in the area subsides, which allows the gingiva to initiate its natural healing process and seal the pockets.

However, if the periodontal pockets remain exposed following completion of scaling and root planing, bacteria in the oral cavity may return to the pockets and create new plaque, which may inhibit the beneficial effect of the procedure and prevent utilization of its full beneficial potential. This is especially crucial in the first few days following scaling and root planing, during which the patient may find it difficult to maintain proper oral hygiene due to gingival pain, bleeding and swelling resulting from SRP.

Pocket-X Gel is intended to prevent this situation and physically shield the periodontal pockets from external bacteria, which would allow the gingiva to promote its healing process and start sealing the pockets.

The study's hypothesis is supported by an *in-vitro* study, which was conducted in order to examine Pocket-X Gel's ability to physically block infiltration of oral pathogens. The oral pathogen chosen for this study was *Porphyromonas gingivalis*, which is considered one the main pathogens involved in periodontitis. In order to determine whether the bacterial-barrier activity of Pocket-X Gel is derived merely from its physical barrier properties, Pocket-X Gel used for the purpose of this study had both of its preservative agents, Octenidine Dihydrochloride and Phenoxyethanol, removed from its formula. The only components included in the studied formula were Pocket-X Gel's physical-acting components, which are responsible for creation of the viscous gel at 37° C: Poloxamer 407 and Hyaluronic Acid, as well as water as a solvent.

As part of this study, four sterile tubes were filled with sterile Peptone Water (PW), under aseptic conditions. Cell strainers were placed upon all four tubes. Two tubes were assigned to the test group and two tubes were assigned to the positive control group. One full

syringe of Pocket-X Gel was then applied upon each cell strainer of the test group tubes. The control group was left untreated. Next, 0.1 ml of *Porphyromonas gingivalis* at a concentration of 1.0×10^6 CFU/mL was applied to each of the cell strainer upon all four tubes. All tubes were then incubated at 37° C for 6 hours under anaerobic conditions. After 6 hours, all cell strainers and tube contents were tested by membrane filtration method. The membrane filters were placed onto TSA Petri plates, which were incubated at 30 - 35° C for 5 days. Results indicated that PW in test group tubes contained no more than 10 CFU per 40 ml, as opposed to CFU values of 4.7×10^3 and 5.3×10^3 per 40 ml of PW in the control group tubes. Cell strainers CFU value was high in both the test and control groups, with values ranging from 1.4×10^3 to 2.2×10^3 . This study indicates that Pocket-X Gel was able to block the infiltration of *P. gingivalis* through the cell strainers and prevent the contamination of the PW in the test group tubes.

4. OBJECTIVES

The overall objective of this study is to assess the safety and efficacy of Pocket-X Gel in the improvement of gingival healing and natural sealing of periodontal pockets in patients with periodontal disease, following scaling and root planing. Safety will be evaluated in accordance with the adverse events reported by participants and oral pathologies recorded by the investigators, compared between segments treated with the studied device and segments untreated with the studied device (in case of localized adverse events) and to adverse events attributed to scaling and root planing based on available literature. Efficacy will be determined in respect to the differences between the measurements taken from segments treated with the studied device and segments that were not treated with the studied device, also taking into account efficacy measurements from similar studies and studies on scaling and root planing, based on available literature.

5. STUDY DESIGN

5.1. OVERALL DESIGN

This study is a single arm, open-label, split-mouth study.

All enrolled participants will initially undergo root planing and scaling on the entire mouth. Following the completion of scaling and root planing, each participant will have one/two of his/her mouth segments (quadrants) treated with Pocket-X Gel. The contralateral segment(s) of the Pocket-X Gel-treated segment(s) will serve as control.

The study hypothesis is that patients treated with Pocket-X Gel following scaling and root planing will exhibit better periodontal pocket healing on their treated segment(s) than their untreated segment(s) as well as compared to data available in the literature concerning the efficacy of scaling and root planing.

The total duration of the study for each participant will be 6-7 months. The study will include a total of 5-7 visits, depending on the number of scaling and root planing sessions required,

based on the severity of each participant's periodontal disease. Follow-up visits will occur 4, 12 and 24 weeks after completion of scaling and root planing and first application of the studied device. Detailed description of each visit is provided under section 5.5 – Visits and Follow-Ups.

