5.2. STUDY ARMS AND INTERVENTION

The study will include a single arm.. Participants will undergo the following intervention and procedures:

- Examination of the gingiva and periodontal pockets and study measurements recording – the following measurements will be taken: pocket probing depth, bleeding index, recession level, clinical attachment level, mobility grade and furcation. Additionally, sub-gingival biofilm samples may be taken from some participants periodontal pockets for the purpose of bacterial testing to quantify three main periodontal pathogens: *Porphyromonas gingivalis*, *Tannerella forsythia* and *Treponema denticola*. Samples will be tested at the periodontal clinic by the investigator or his/her assistants, using a BANA-Zyme test kit (OraTec Corp., USA).
- 1-4 sessions of scaling and root planing (SRP) on the entire mouth.
- Dividing the mouth into segments (split-mouth) – one/two segments (quadrants) that will be treated with Pocket-X Gel following SRP and two/three segments (quadrants) that will not undergo any further treatment beyond SRP. The number of treated segments and untreated segments will be decided by the investigators and is dependent on the clinical symmetry between the contralateral segments of each participant.
- 1-2 prophylaxis and oral hygiene instruction sessions.
- 1-3 sessions of treatment with Pocket-X Gel, which will be applied to periodontal pockets present in one/two of the pre-determined mouth segment(s) – administration will be performed by applying the product into the periodontal pockets, through a thin plastic tip attached to a syringe containing Pocket-X Gel. More information regarding Pocket-X Gel administration can be found under section No. 5.3 of this protocol.

Section 5.5 of this protocol provides information regarding the interventions and procedures that will be performed at each study visit.

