5.6. RESTRICTIONS

In order to obtain reliable safety and efficacy results from the study, participants will be requested to refrain from undergoing any additional unnecessary periodontal treatments during the course of the study, aside from those provided as part of the study.

In cases that such additional treatment is deemed necessary, the participants will be requested to report the treatment details to the study investigators, who will record them.

Participants will also be requested to follow the instructions on maintaining good oral hygiene they receive from the investigators at the beginning of the study, and refrain from changing this routine. An exception will be made during the 2 days following treatment with Pocket-X Gel, during which participants treated with the product will be requested to brush their teeth very gently and not use dental accessories such as dental floss, in accordance with the manufacturer's instructions.

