10. CALIBRATION OF EXAMINERS

The study's investigators – two experienced periodontists, will be calibrated for scaling and root planning procedures and recordings of clinical data to ensure that all clinical procedures will be standardized according to the study protocol and to minimize both intra and inter-examiner variability across the time points. The two examiners will be calibrated initially for PPD and CAL according to the method of Jeffcoat et al. (1). Briefly, as part of the calibration exercise, each of the 2 examiners will measure PPD and CAL 2 time at 10 sites (PPD>5 mm) in each of 5 patients. For both examiners and all 25 sites, the mean absolute will be <0.5 mm for both parameters.

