12. ADVERSE EVENTS

During each visit, participants will be asked whether they experienced or experience any adverse events. In case that an adverse event has occurred, investigators will record all details of the event and will assess whether the event may be related to the studied device.

Any new pathologies observed by the investigators that did not exist at baseline or have worsened since baseline, will be considered adverse events and recorded accordingly.

Participants will be requested to report any serious adverse events immediately to the investigators, without waiting for the next visit.

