16. RESPONSIBILITIES

16.1. INVESTIGATORS RESPONSIBILITY

Study Investigators will be responsible for the following:

- Ensuring that the investigation is conducted in accordance with the study protocol and applicable regulations of the local regulatory authority.
- Obtaining an informed consent from every participant.
- Reporting unexpected or serious adverse events to the sponsor.
- Supervising the use of the device. The study investigators shall permit the device to be used only by themselves or qualified dentists.
- Maintaining study records.
- Providing the sponsor with study records required for monitoring, statistical analysis, safety evaluation, scientific reporting and regulatory obligations.

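### Nothing in the text reviewed requires the examiner to be unaware of the gel side or says how that side is chosen, so a side-dependent reading error could pass for a gel effect

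*Combined protocol and SAP*

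**What the plan says.** All references are to the combined protocol and SAP.

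- **Design (section 5.1):** "This study is a single arm, open-label, split-mouth study". The control is the opposite side of the same mouth, which has SRP and nothing further. No sham gel is described. Section 4 judges efficacy by the difference between treated and untreated segments, with published results as additional context.
- **Who measures (section 10):** of the investigators it says: "two experienced periodontists, will be calibrated for scaling and root planning procedures and recordings of clinical data". The agreement target reads: "the mean absolute will be <0.5 mm for both parameters"; the noun after the word absolute is missing.
- **Who applies the gel (section 16.1):** "The study investigators shall permit the device to be used only by themselves or qualified dentists".
- **What shares a visit (Table 1, section 5.5):** Follow-ups 1 and 2 each contain the study measurements and an optional further gel application. No rule says that measurement comes first.
- **Adverse events (section 12):** "During each visit, participants will be asked whether they experienced or experience any adverse events". The interviewer is not named. If an event has occurred, "investigators will record all details of the event and will assess whether the event may be related to the studied device".
- **Choice of segments (section 5.2):** "The number of treated segments and untreated segments will be decided by the investigators and is dependent on the clinical symmetry". This covers how many segments are treated. Section 5.3 and Table 1 treat the gel segments as settled beforehand but give no method for settling which side.
- **Analysis (section 15.2):** paired t-test or signed rank test of treated against control, two-tailed at 5%.

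The text reviewed lacks whatever stands between section 10 and section 12.

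**The concern.** Pocket depth, attachment level and bleeding are read by an operator at the chairside. As the plan stands, the same periodontist may apply gel to one side of a mouth and later probe both sides. An examiner who knows the side can, without any intent, read it slightly more favourably. In a split-mouth design such an error does not average out over participants, because it always points towards the gel. It therefore enters the paired difference in full. No test in section 15.2 can separate it from a real effect, and more participants would make a false result more likely.

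The unstated choice of side is a second and smaller matter. If investigators may choose, the gel side could differ systematically from its control at baseline.

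**Working it through.** **1. The plan's own figure.** Section 15.1 gives effect size 0.5, standard deviation of differences 1.0, one-sided 5% and 80% power. The exact paired t-test (noncentral t, n − 1 degrees of freedom) first reaches 80% at n = 27, where power is 81.2%. Allowing for dropout, 27 / (1 − 0.20) = 33.75, so 34. Both planned figures reproduce.

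**2. What a reading error does.** Suppose the gel has no effect. Let b be the net error in favour of the gel side in the between-side difference in change, that is, the side-dependent error at follow-up minus any at baseline. An equal error at both times would cancel. If baseline is read before the side is known, b is the whole follow-up error. The paired t statistic then has noncentrality b × √27 / 1.0 on 26 degrees of freedom. The test is two-sided at 5%, as in section 15.2.

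| Assumed b | Share of planned 0.5 | Noncentrality | Significant, either direction | Significant, favouring gel |
|---|---|---|---|---|
| 0 | 0% | 0 | 5.0% | 2.5% |
| 0.1 | 20% | 0.52 | 7.9% | 7.2% |
| 0.2 | 40% | 1.04 | 17.0% | 16.9% |
| 0.3 | 60% | 1.56 | 32.4% | 32.3% |

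An observed mean difference of about 0.40 is enough for significance. Under the one-sided 5% test assumed in section 15.1, the chances for b = 0, 0.1, 0.2 and 0.3 would be 5.0%, 12.7%, 26.4% and 45.0%. The mismatch in sidedness between sections 15.1 and 15.2 is a separate matter, and this point does not depend on it.

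Section 15.1 gives no unit for 0.5 or 1.0; millimetres are assumed. The values of b are also assumed, since the documents contain no estimate of reading bias.

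**3. Choice of side.** Assume the contralateral baseline difference has a standard deviation of 0.3 to 0.7 mm, and each extra mm of depth brings 0.3 to 0.5 mm more reduction. If the deeper side receives gel in a proportion p of participants, the mean bias is (2p − 1) × √(2/π) × SD × slope. At p = 0.6 its upper end is 0.2 × 0.798 × 0.7 × 0.5 = 0.056 mm. Simulated rejection rates with an inert gel are 5–6% at p = 0.6, 5–11% at p = 0.75 and 6.5–31% at p = 1. The symmetry condition in section 5.2 makes the last case unlikely.

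**4. Would gel residue reveal the side?** Section 3.2 says the gel stays 1–3 weeks, and Table 1 allows ±14 days.

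- Follow-up 1 can fall at week 4 − 2 = 2, when gel may still be present.
- Follow-up 2 comes at least (12 − 2) − (4 + 2) = 4 weeks after a re-application at Follow-up 1.
- Follow-up 3 comes at least (24 − 2) − (12 + 2) = 8 weeks after one at Follow-up 2.

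On the plan's own figures, residue should not give the side away at the last two visits.

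**The case against.** **The design is openly declared.** It is. But open-label treatment does not rule out an examiner who is unaware of the side, and the text reviewed neither provides for one nor explains why not.

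**Calibration covers it.** Calibration is aimed at variability within and between examiners. It does not hide the side. A reader might also set the assumed biases against the 0.5 mm target and conclude that the plan tolerates them. That does not follow: a limit on absolute error in site readings is not comparable with a directional error in a between-side mean, and the sentence stating the limit is incomplete.

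**The literature comparison is a safeguard.** It is conditional on data being available, and section 15.2 does not say which side is compared. A favourable error on the gel side would leave a comparison of control with literature unchanged and make the gel look better than published SRP.

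**The order of events is clear enough.** This partly stands. Section 5.2 and Table 1 both list examination, then SRP, then division of the mouth, then gel, so baseline readings before designation are the natural reading. The documents do not, however, fix when the side is chosen or put follow-up probing ahead of re-application.

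**Some routes to unmasking are inferred.** This stands. A reader might take section 12 to mean that the investigators themselves question participants about adverse events; it names no interviewer and gives investigators only the recording and the judgement of relatedness. Likewise, section 5.6 says "participants treated with the product will be requested to brush their teeth very gently", which names no side and so does not show that participants know theirs.

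**Side choice adds little.** On the figures above, that is fair. It is a secondary point.

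**Conclusion.** The point holds for the text reviewed. One person may apply the gel and probe, nothing requires that person to be unaware of the side, and no method for choosing the side is given. With an inert gel, 27 completers and a standard deviation of differences of 1.0, assumed reading errors of 0.1, 0.2 and 0.3 raise the two-sided false-positive rate from 5% to 8%, 17% and 32%.

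These figures show what a bias could do. A reader might infer that such a bias will occur or that the examiner is certain to have applied the gel. The documents support neither: section 16.1 also allows other qualified dentists to apply it. Nor do they support treating the choice of side as an equal threat, given the symmetry condition.

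This should be fixed, and before data collection, because analysis cannot repair it afterwards. The conclusion is conditional on the unavailable text between sections 10 and 12: if it sets masking or allocation, the point lapses to that extent.

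**What to change.** 1. **Section 10 and Table 1.** For each participant, the calibrated periodontist who did not apply the gel does the probing at baseline and every follow-up. Probing comes before any re-application and without access to gel or adverse-event records. The other periodontist handles the adverse-event assessment. The examiner records a guess of the gel side, so that the success of masking can be reported.
2. **Section 5.2 and Table 1.** The investigators first record which contralateral pairs are symmetric enough to use. The gel side of each pair is then randomised by concealed list or envelope, opened only after baseline probing and the end of SRP.

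**Cost.** A protocol amendment, a randomisation list or envelopes, and scheduling of both periodontists for each participant. The scheduling is a real constraint, eased because section 16.1 lets a qualified dentist apply the gel. No extra visits or participants are needed. Masking may be incomplete, most of all at Follow-up 1, where gel may still be visible, and because a participant may disclose the side. The recorded guesses would help show how often masking fails, although a real benefit could also lead to correct guesses.
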